6.3.2 Exclusion Criteria

Subjects will be excluded if presenting at least one of the following:

- 1) Indeterminate or not classified colitis.
- 2) Current or previous participation in interventional clinical trials (within the last 3 years).
- 3) Presenting mental incapacity, unwillingness or language barriers precluding adequate understanding or cooperation.

- 4) Hospitalized patients at Day 1.
- 5) Current off label treatment with Vedolizumab.

6.3.3 Study Discontinuation Criteria

It will be considered a premature termination the situation in which the subject discontinues the participation, i.e. they are withdrawn from the study before completing the 12 months of follow up period (365 days \pm 14 days from Day 1), due to any of the reasons listed below:

1. Withdrawal of consent: subjects who for any reason withdraw the free and informed consent;
2. Lost to follow-up (no return of the subject on the expected date of visit - drop-out from the protocol);
3. Death;
4. Study termination;
5. Any situation that places the subject within one of the exclusion criteria.

Note: Patients who are eligible for the prospective period, it means, with active disease at Day 1 but who during the 12 months period presents disease remission and/or no activity disease condition, are allowed to continue the participation in the study.

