- Enrolment – with the exclusion of patients with indeterminate or not classified colitis and that have participated in interventional clinical trials during the last 3 years. In fact, during a trial the subject has access to special and specific treatment and diagnosis procedures. The participation in an interventional trial during the previous 3 years may cause misunderstanding about treatment patterns and resources utilization, because in this project the retrospective data will be collected exactly about this period.
- Statistical analysis – with the inclusion in the logistic regression models of variables associated with both disease control and other variables of interest.

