6.3.1 Inclusion Criteria

Subjects must meet all of the following inclusion criteria:

- 1) Male or female;
- 2) Subjects aged 18 years or older (at the time of diagnosis of moderate to severe UC or CD);
- 3) Diagnosis of moderate to severe CD or UC for at least 6 months prior to Day 1 appointment according the clinical or endoscopic criteria (23, 24, 25, 26, 27);
- 4) Subjects who provided the written informed consent.

In addition, for the prospective period, eligible patients should present at least one of the following criteria that will only be applied at Day 1:

- For CD patients:
 - HBI \geq 8 or
 - CDAI \geq 220 or

Considering that for CD patients, the disease activity may not be clearly documented only with clinical data, some objective criteria may be considered as entry criteria for the 12-month prospective period:

- colonoscopy in the previous year suggestive of inadequate control of activity
or
- calprotectin levels in the previous year suggestive of inadequate control of activity (i.e. calprotectin >200ug/g) (28).

For UC: partial Mayo Score ≥5

Note 1: UC patients with no or mild disease activity at Day 1 will not continue to follow up. CD patient with no or mild disease activity at Day 1 but with colonoscopy or calprotectin levels (i.e. calprotectin >200ug/g) in the previous year suggestive of inadequate control of activity will progress to 12-month follow up.

Patients that fulfill the above criteria (active disease) will be followed for 12 months, in order to explore patterns of care.

Note 2: Patients with colostomy and prospective period:

Although clinical scales defined above are impacted by colostomy these patients will not be excluded from the protocol to ensure the assessment of different clinical presentations of the IBD. In addition, patients with colostomy must follow the same criteria as above to be eligible to the prospective phase.

Note 3: Patients who are eligible for the prospective period, it means, with active disease at Day 1 but who during the 12 months period presents disease remission and/or no activity disease condition, must continue in the study.

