8.4 Other Safety Information

If the investigator becomes aware of any of the following events associated with a Takeda product during the study, whether or not associated with an AE, the event should be recorded on an AE Report form /Pregnancy Report form and submitted to the Sponsor within 24 hours of investigator awareness.

- **Use during pregnancy**
- **Overdose:** This refers to the administration of a quantity of a drug given per administration or cumulatively, which is above the maximum recommended dose according to the authorised product information. Clinical judgement should always be applied.
- **Off-label use:** This relates to situations where the drug is intentionally used for a medical purpose not in accordance with the authorised product information.
- **Misuse:** This refers to situations where the drug is intentionally and inappropriately used not in accordance with the authorised product information.
- **Abuse:** This corresponds to the persistent or sporadic, intentional excessive use of a drug, which is accompanied by harmful physical or psychological effects.

- **Medication error:** This refers to any unintentional error in the prescribing, dispensing, or administration of a drug while in the control of the healthcare professional or patient.
- **Accidental occupational exposure:** This refers to exposure to a drug, as a result of one's professional or non-professional occupation.

9 Data Quality Control and Assurance

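### Patients who enter a trial or start off-label vedolizumab after Day 1 are withdrawn without a month-12 score, and the printed 12-month fraction then counts them as not active

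*Protocol*

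**What the plan says.** Protocol 6.3.3 defines premature termination as the case where patients stop early, in that "they are withdrawn from the study before completing the 12 months of follow up period". The fifth listed reason is "Any situation that places the subject within one of the exclusion criteria". SAP 4.3 repeats it.

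The exclusion criteria are in Protocol 6.3.2 and SAP 4.2. Criterion 2 is current participation in an interventional trial, or participation within 3 years. Criterion 5 is "Current off label treatment with Vedolizumab". Criterion 4 is tied to one date: "Hospitalized patients at Day 1". Criteria 2 and 5 carry no such limit.

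The study flow chart (Protocol 7.1, Table 1) marks exclusion criteria at Day 1 only. It schedules disease activity at Day 1 and at month 12, with no assessment at withdrawal.

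On patients who improve, Protocol 6.3.1 Note 3 says that a followed patient who "presents disease remission and/or no activity disease condition, must continue in the study". The note at the end of 6.3.3 uses weaker wording: it permits them to stay.

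Protocol 10.3 divides the number active after 12 months by all patients active by score at Day 1. The SAP counterpart is blacked out. Protocol 10.5 imputes nothing outside the questionnaires, and SAP 7.7 replaces nothing.

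**The concern.** The study sets out to describe the 12-month course of active disease and what drives physicians' treatment decisions in routine practice. Moving a patient into a trial, or to off-label use of a drug, is such a decision. Under reason 5 it ends observation.

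Once withdrawn, the patient has no month-12 score, and neither document says how a patient without one is counted. The SAP keeps everyone who entered follow-up in the longitudinal population (7.2). Read with the printed fraction, a withdrawn patient stays in the denominator and can never enter the numerator. The month-12 logistic models lose the patient's outcome. In the time-to-control analysis the patient is one more early exit that may be related to prognosis.

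The flow chart adds to the problem. It checks exclusion criteria at Day 1 only, while reason 5 applies them throughout, so sites may act differently.

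**Working it through.** **Inputs from the documents**

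- Planned follow-up: 40–60 CD and 30–50 UC patients (Protocol 10.6, SAP 6).
- Enrolment target: at least 30 active patients per disease (Protocol 6.3.4).
- Denominator: all patients active by score at Day 1 (Protocol 10.3).

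**The plan's own cohort figure**

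400 × 0.50 × 0.20 = 40 and 400 × 0.50 × 0.30 = 60 per disease. This reproduces 40–60 for CD. It does not reproduce 30–50 for UC. That mismatch is a separate matter. Denominators of 30 to 60 are used below.

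**Formulas**

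Let f be the share withdrawn under reason 5. Let q_out and q_in be the proportions active at month 12 among withdrawn and retained patients.

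- Full follow-up: f·q_out + (1 − f)·q_in
- Printed fraction: (1 − f)·q_in, so the error is −f·q_out
- Scored patients only: q_in, so the error is −f·(q_out − q_in)

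The printed fraction is too low whenever any withdrawn patient is active. The complete-case figure is too low only if q_out exceeds q_in.

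**Cost per patient, printed fraction**

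Each withdrawn patient who is truly active costs 1/30 = 3.3 points, 1/40 = 2.5, 1/50 = 2.0 or 1/60 = 1.7.

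**Illustration**

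The documents give no withdrawal rate, so this is an assumption: 50 followed patients of one disease, 30 (60%) truly active at month 12. Of w withdrawn, a are active. The printed fraction is (30 − a)/50 and the complete-case figure is (30 − a)/(50 − w).

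| w | a | Printed fraction | Scored patients only |
|---|---|---|---|
| 2 | 2 | 28/50 = 56% | 28/48 = 58% |
| 5 | 5 | 25/50 = 50% | 25/45 = 56% |
| 8 | 8 | 22/50 = 44% | 22/42 = 52% |
| 5 | 3 | 27/50 = 54% | 27/45 = 60% |
| 8 | 4 | 26/50 = 52% | 26/42 = 62% |

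In the first three rows every withdrawn patient is active, which is the extreme case. In the fourth, withdrawn patients are active at the overall 60% and the complete-case error is zero. In the fifth they are active less often and the complete-case figure is too high. The printed fraction is too low in all five.

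**Wider range, also assumed**

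With f = 5–20%, q_in = 30–50% and q_out = 70–100%:

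- Complete-case error, smallest: 0.05 × (0.70 − 0.50) = 1 point. Largest: 0.20 × (1.00 − 0.30) = 14 points.
- Printed-fraction error: 0.05 × 0.70 = 3.5 points to 0.20 × 1.00 = 20 points.

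**Against sampling error**

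The 95% half-width at p = 0.5 is 1.96·√(0.25/n): 17.9 points at n = 30, 13.9 at 50 and 12.7 at 60. The errors approach or exceed it only towards the top of the assumed range.

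**Does anything planned recover these patients?**

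The one longitudinal sensitivity analysis (SAP 8, item 7) accepts scores from the 30 days up to day 365. It cannot supply a score for someone withdrawn before that window, for example at month 5. Disposition (SAP 7.3) and Listing 2 show the withdrawals but do not change the estimate.

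**The case against.** A reader might infer that the plan selectively removes treatment failures while holding on to patients who remit. The documents do not support that. Reason 5 does not depend on disease activity: a patient in remission who enters a trial is withdrawn too, and an active patient who meets no exclusion criterion stays. Note 3 only confirms that the activity entry criteria apply at Day 1. It is plausible that patients move to trials or off-label use because their disease is uncontrolled, but neither document says so, and some may be controlled by month 12.

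A reader might also infer that the trial exclusion has no purpose after Day 1, since Protocol 6.2 justifies it "because in this project the retrospective data will be collected exactly about this period". The same paragraph first gives a general reason: trial patients receive special treatment and diagnostic procedures. That reason applies to follow-up as well, so ending routine-care observation at trial entry can be defended. It does not settle how the withdrawn patient is counted.

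Nor is the treatment decision necessarily lost. Follow-up data are gathered quarterly with reasons for discontinuing treatment (Protocol 7.1, 7.2), so the switch may be recorded before withdrawal. Section 8.4 does not show that off-label use is expected. It is a conditional safety clause on sponsor products.

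Finally, the larger errors come from the printed denominator together with the lack of a rule for missing scores. Consent withdrawal, loss to follow-up and death are exposed in the same way. This is correct, but reason 5 differs in that the plan itself creates the loss and can avoid it.

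**Conclusion.** The concern holds for the secondary 12-month results. Under the printed fraction, each patient withdrawn under reason 5 who is truly active at month 12 lowers the active proportion by one patient, about 2 to 3 points at 50 to 30 patients. This needs no assumption about whether withdrawn patients are sicker than the rest. It does assume that the fraction is applied as printed; the blacked-out SAP formula cannot be checked.

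If only scored patients are analysed, a downward error requires that withdrawn patients be more often active than retained ones. If they are equally active there is no error, and if less active the error reverses. The number of such withdrawals is not given and may be small. The primary Day 1 proportions are unaffected. The change is worth making because it is cheap and removes an avoidable ambiguity.

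**What to change.** In Protocol 6.3.3 and SAP 4.3, state that exclusion criteria 2 and 5 are entry criteria applied at Day 1 only. A patient who meets one later stays under observation unless consent is withdrawn. Record the event as a dated treatment change with its reason, and collect the month-12 activity score where a visit or record provides it. This alters observation only, not treatment.

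In the SAP:

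- Report the 12-month proportion with these patients included as observed.
- Add a sensitivity analysis that counts them as not controlled on routine care.
- State how a patient without a month-12 score is counted, so that none is silently taken as not active.

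Reconcile 6.3.1 Note 3, which obliges patients in remission to stay, with the 6.3.3 note, which only permits it.

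If follow-up can no longer be changed, the three SAP items can still be added.

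The cost is wording in two documents and one more analysis. The downside is that a few month-12 scores will reflect trial or off-label treatment and some may be unavailable, particularly for patients treated in a trial elsewhere. The sensitivity analysis covers both.

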6.3.4 Enrolment

Each Study Site Responsible (Investigator) should include consecutive subjects who meet eligibility criteria, from patients attending pre-scheduled routine medical appointments.

The expected recruitment of study subjects will occur during a 6 month period. A patient tracking log form will be used by each site.

Subjects should be included in the study only once. Data erroneously collected from subjects for which written consent is not available, will not be included in or will be deleted from the database.

After 2 and 4 months of enrolment, the overall proportion of patients with CD and UC will be reviewed. In case the expected ratio of IBDs (50%CD/50%UC) is not attained at 2 and 4 months of enrolment, the participating sites will be instructed to change future enrolments so

that this balance is achieved and that at least 30 UC patients and 30 CD patients with active disease enter the prospective follow-up.

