6.2 Discussion of Study Design

This is a non-interventional study designed to evaluate disease control, treatment patterns, burden of disease and health related quality of life among patients with IBD. The cross-sectional design with no control group is suitable and feasible to address the study objectives, which are mainly descriptive. Furthermore, the inclusion of a prospective follow-up for patients with active disease will enable an insight on how active CD or UC are managed in Brazil and what are the factors associated to achieving disease control.

In terms of external validity, two major points should be considered. First, the 20 study sites will be selected among reference public and private institutions for IBD management. It is expected that their patients will be representative of patients with moderate to severe IBD in Brazil. In addition, the inclusion and exclusion criteria are not restrictive and will enable the assessment of real-world data about IBD control in Brazil. Internal validity will be reinforced by training of Investigators and the use of same study procedures and forms. Hence, observation bias is not expected to occur during the cross-sectional and prospective evaluations. Although retrospective data collection is challenged by the quality of medical records, treatment patterns and hospitalizations are frequently recorded and no significant missing data is expected, which could lead to underestimation of health care utilization data. In addition, it is expected that completeness of medical records will be high in the last 3 years (retrospective period), namely regarding the use of biological treatments.

Because this is an observational study, some limitations should be minimized. All eligible patients will be consecutively invited to the study and the enrolment period will be of 6 months. Disease control may be underestimated due to selection bias, since patients with active IBD are expected to have more medical appointments and may be more easily invited. Nevertheless, the 6-month period will also enable the inclusion of patients with no or mild active disease.

Potential confounders will be addressed at:

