10.1.2 Statistical analyses overview

Descriptive statistics will be calculated for all variables, including mean, median, standard deviation and range for numerical variables and absolute and relative frequencies for categorical variables. Whenever relevant, 95% confidence intervals (CI) will be computed. For each study endpoint, data will be summarized by IBD type (CD and UC).

Cross-sectional analysis

The cross-sectional analysis will be conducted once all patients have completed the Day 1 assessment (expected to occur 6 months after start of enrolment).

This analysis will allow a characterization of the study population, the estimation of primary endpoints and to compare the subgroup of patients with no or light activity of disease and those with moderate to severe activity. Hence, for each IBD type, the patients with disease activity will be compared with patients with no or light activity regarding socio-demographic, clinical and treatment variables of interest. Chi-square or Fisher exact tests will be used to compare activity vs non-activity regarding qualitative variables and t-student / Mann-Whitney tests will be used for comparison of quantitative variables. If applicable, logistic regression will be used for evaluating associated variables. All tests will be two-sided considering a significance level of 5%.

Longitudinal analysis

The longitudinal analysis will be performed once all the patients that were included in the prospective period have completed the 12-month follow up.

The proportion of controlled patients will be presented as well as the 95%CI at the 12-month follow up assessment. If applicable, logistic regression will be used for calculating odd ratios and 95% confidence intervals for the patient control at month 12 determined by independent variables. All tests will be two-sided considering a significance level of 5%.

In case the expected ratio of IBDs (50%CD/50%UC) is not attained at 2 and 4 months of enrolment, the participating sites will be instructed to change future enrolments so that this balance is achieved and that at least 30 UC patients and 30 CD patients with active disease enter the prospective follow-up.

For details of the statistical analyses please refer to the Statistical Analysis Plan.

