10.6 Determination of Sample Size

It is expected to include approximately 400 patients regardless of IBD type. This sample size will allow estimates with 95% confidence interval and a margin of error less than 5%.

Based on the above and considering an expected ratio of CD/UC of approximately 50%/50%, and that the rate of inadequate control of disease activity varies from 20-30% (regardless of the IBD type), it is expected to analyze 40-60 patients with CD and 30-50 patients with UC during the 12-month follow up.

11 Reports

A Non-Interventional Study Report based on the results obtained will be prepared and submitted to Global Research for distribution. The Final Study Report should be available within one year from collection of the last data point, and the participating sites should be informed about the results when the report is finalized.

12 Publications

Takeda aims to have the results of this study published.

Takeda has the right to use the data and results for regulatory purposes and for internal presentation within the company and to partners.

13 Archiving of Study Documentation

During the course of the study the Site Responsible must as a minimum file the essential documents (Section 4.4), the protocol, any amendments, the list of participating subjects, the written informed consents, the CRFs and the progress reports in the Study Site File. After final database lock the Site Responsible must as a minimum store the list of participating subjects and the signed Informed Consent Forms on site for 5 years. The Site Responsible should store additional study documentation for a longer period of time as required by any local regulations and/or hospital requirement.

14 References

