## 7.2 Analysis Sets

In this study, they will be analyzed two populations:

- The cross-sectional population will include all patients who have completed the Day 1 assessment (expected to occur 6 months after start of enrolment).
- The longitudinal population will include all patients included in the prospective period (patients with active IBD in Day 1).

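### Could the target of 30 active patients per disease bias the primary proportion with active disease?

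*Protocol*

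**What the plan says.** Protocol section 6.3.4 sets the basic rule: each site "should include consecutive subjects who meet eligibility criteria, from patients attending pre-scheduled routine medical appointments". Section 6.2 repeats it: "All eligible patients will be consecutively invited to the study and the enrolment period will be of 6 months".

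Section 6.3.4 then has the overall CD/UC split reviewed after 2 and 4 months. If the 50/50 ratio has not been reached, sites are told to alter later enrolment so "that this balance is achieved and that at least 30 UC patients and 30 CD patients with active disease enter the prospective follow-up". Section 10.1.2 repeats the instruction in almost identical terms: "instructed to change future enrolments so that this balance is achieved and that at least 30 UC patients and 30 CD patients". There too, the 30 per disease are patients whose disease is active at entry to follow-up. Neither section says how the 30 are to be found, or restates that enrolment stays consecutive within each disease.

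The primary endpoints are the proportions active at Day 1, estimated separately in CD and UC. On the analysis set, SAP 7.2 states: "The cross-sectional population will include all patients who have completed the Day 1 assessment". SAP 7.5 computes the primary proportions in that set.

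**The concern.** The instruction has two parts that behave differently. Steering by disease type cannot bias a proportion estimated within one disease. Steering by activity can. For UC, entry to follow-up (partial Mayo of 5 or more) is identical to the primary numerator, so a quota on follow-up entrants is a quota on the endpoint. For CD the overlap is partial, because section 6.3.1 also admits to follow-up a "CD patient with no or mild disease activity at Day 1 but with colonoscopy or calprotectin levels" from the past year that suggest poor control.

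The protocol is alert to this kind of bias. Section 6.2 warns: "Disease control may be underestimated due to selection bias, since patients with active IBD are expected to have more medical appointments". Its remedy is consecutive invitation over six months. Seeking out active patients after month 2 or 4 would push in the same direction and weaken that remedy. Every such patient would count in the primary proportion, which would then partly reflect a recruitment target. The SAP does not ask for a record of whether an instruction was issued.

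**Working it through.** **Inputs.** About 400 patients in total (Protocol 10.6). The same section gives the split and the rate: "considering an expected ratio of CD/UC of approximately 50%/50%, and that the rate of inadequate control of disease activity varies from 20-30" per cent. The floor is 30 active patients per disease (6.3.4, 10.1.2). How sites would react to a shortfall is not stated; I assume they top up to exactly 30, replacing other patients.

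**The plan's own figures.**
- Precision: 1.96 × √(0.5 × 0.5 / 400) = 4.9 points, so the stated margin below 5% holds for the pooled sample.
- Patients per disease: 400 × 50% = 200.
- Expected active: 200 × 20% = 40 and 200 × 30% = 60. This reproduces the 40-60 CD patients expected in follow-up.
- The UC range of 30-50 does not follow from 200. It fits about 160, since 160 × 20% = 32 and 160 × 30% = 48. I therefore run both sizes.

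**Does the floor bind, and by how much?** Let X be binomial(n, p), the number active under consecutive enrolment. The chance of a shortfall is P(X < 30). The mean shift in the reported proportion is E[max(30 − X, 0)] / n. The half-width is 1.96 × √(p(1 − p)/n).

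| n | p | P(X < 30) | Mean shift (points) | 95% half-width (points) |
|---|---|---|---|---|
| 200 | 20% | 2.8% | 0.04 | 5.5 |
| 200 | 25% | 0.02% | 0.00 | 6.0 |
| 200 | 30% | about 0 | 0.00 | 6.4 |
| 160 | 20% | 31.6% | 0.72 | 6.2 |
| 160 | 25% | 2.5% | 0.04 | 6.7 |
| 160 | 30% | 0.04% | 0.00 | 7.1 |

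These shifts are averaged over all samples, as if the instruction were always in force. It applies only when the ratio is missed, so they overstate the expected effect.

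**When the floor does bind.** At n = 200 and p = 20% the mean shift given a shortfall is 0.036 / 0.0283 = 1.3 points, or about 2.5 patients. Topping up then gives 30/200 = 15%; with 160 patients it gives 30/160 = 18.75%. Both lie below 20%, the bottom of the planned range. In a sample where the floor binds, the estimate was already low by chance, and the top-up does not carry it past the true rate.

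**What a visible shift would need.** A mean shift of 1 point requires a disease group of 154 or fewer at 20%, 126 or fewer at 25%, or 106 or fewer at 30%. Alternatively, with 200 patients, activity would have to be about 15% (chance of a shortfall 47%, shift 1.0 point), which is below the planned range. A group that small is also the imbalance the instruction exists to correct.

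**CD.** If patients entering by colonoscopy or calprotectin count towards the 30 without being in the primary numerator, the CD shifts are upper bounds.

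**The case for a change.** The best case for acting is that the text sets a floor without a cap, so the reassurance depends on sites stopping at 30. Suppose instead that the odds of enrolling an active patient doubled in the last third of enrolment. At 20% the active share in that third becomes 0.4/(0.4 + 0.8) = 33.3%, and the overall shift is (33.3 − 20)/3 = 4.4 points. At 30% the same steps give 46.2% and 5.4 points. Either is close to the half-width, and would add to a bias that section 6.2 already expects.

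The arithmetic is right, but the doubled odds are an assumption with no basis in the documents. Several things count against it. The review at months 2 and 4 looks only at the CD/UC split. Consecutive enrolment is required in the same section and is not withdrawn. Recruitment is from routine appointments already booked, Table 1 records activity and follow-up eligibility at Day 1, and no earlier activity screen is described. A physician may know how a patient has been lately, so selection is not impossible, but the plan does not ask for it. The natural reading is that 30 active patients is what a balanced, consecutive sample should deliver: it is the lower end of the plan's UC range.

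What stands is narrow. The two sections are silent on how the 30 are reached, and nothing shows whether an instruction was ever issued.

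**Conclusion.** No change is needed. The wording leaves a detail unsaid, and the consecutive rule beside it supplies the sensible answer: steer the disease mix and take patients as they come within each disease. Followed that way, the primary proportions are unaffected. Even with topping up to 30, the expected shift is 0.04 points at 200 per disease and 20% activity, and 0.72 points at 160. This rests on activity of 20-30%, group sizes of 160 or more, and sites stopping at the floor.

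The possible remedies would gain nothing. SAP section 8 says Amendment 1 was implemented at the end of recruitment in one centre and after it elsewhere, so new enrolment wording could not alter who was enrolled. Leaving out-of-sequence active patients out of the primary proportions would remove only active patients, and could bias the estimate downward if some would have been reached in turn. Repeating the analysis in patients enrolled before an instruction would, at 25% activity and even accrual, widen the half-width from 6.0 points (200 patients) to 7.4 (133, cut at month 4) or 10.4 (67, cut at month 2), to check a shift of almost nothing. If an instruction was issued, the study report can say so alongside disposition without amending the plan.
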